5.11 Interim analyses

There are no planned interim analyses that would question the continuation of the trial. If an unplanned interim analysis should be conducted, it would be described in a separate document REACH WP3_IAP. Interim data reports have been provided to the Data Monitoring and Ethics Committee without formal stopping rules in place.

5.12 Subgroup analyses

Further analysis of the primary and secondary outcomes will be performed for the following subgroups:

- a) Ethnicity.
- b) Women receiving intervention prior to the Covid-19 lockdown vs women receiving intervention after lockdown (March 18th 2020).
- c) Vulnerability as defined by the presence of any of the factors below (further information on the definition of vulnerability can be found in the appendices). We will also test the interaction with a vulnerability index which will be made up as the sum of the same criteria:
 - Age those participants under 20 (Baseline Questionnaire 16-19 years)
 - **Ethnicity** any participant NOT identifying as White-British, White-Irish or White-Other (Baseline Questionnaire) (See Table 2 for full list of categories).
 - **Deprivation** any participant living in a postcode falling in the most deprived areas in England measured through Index of Multiple Deprivation by participant postcode (found on the Participant Information Form).
 - Limited English Proficiency any participant who indicated that they do not have any English language proficiency OR do not speak English well ('not well'/'not any' categories Baseline Questionnaire) OR if 'need an interpreter' is ticked 'yes' on the Participant Information Sheet.
 - Social Complexity those participants who have been classified at booking as having 'intermediate' or 'intensive' social risk factors (Routine Data Social Risk Profile). Social risk factors include lifestyle issues (alcohol use; substance use); recent migrant (<12 months); Refugee/asylum seeker; can't speak English; under 20 years old; domestic violence).

In order to perform the subgroup analyses, the same models for the main analyses will be used but will include an interaction term between the outcome of interest and the subgroup in question If the resulting tests for interaction are significant, then we will consider differences between individual subgroups. The purpose of the subgroup analyses will be solely for hypothesis generation due to the potentially low power of the tests for interaction. For each subgroup analysis we will report the numbers in each subgroup, summary statistics by subgroup, treatment estimates with 95% confidence intervals for each subgroup, and a p-value for the test of interaction (t-test or likelihood-ratio test).

5.13 Complier Average Causal Effect (CACE) analysis

To further assess the effect of the primary outcome healthy baby composite, the intention to treat main analysis will be compared with a Complier Average Causal Effect (CACE) analysis estimating a 'per-protocol' treatment effect. The CACE analysis will repeat the primary outcome analysis using only those participants who complied. Intervention compliance is defined as attending **three** or more antenatal circles. Further information on the definition of compliance can be found in appendix 8.2. CACE estimates are used to build upon causal modelling frameworks to yield causal estimates of the effects of intervention for individuals who comply with treatment (in our case group antenatal sessions) compared to those who would have complied in the control group. CACE effect estimates for compliance, as opposed to intention to treat, will be generated using two-stage least squares (i.e. method of instrumental variable).

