5.16.3 The tenability of the exclusion restriction assumption

The tenability of the exclusion restriction assumption (that the intervention effect is zero for non-compliers) in the CACE analysis will be assessed using a sensitivity analysis. Instead of restricting the intervention effect estimate amongst non-compliers to zero (as specified in the primary CACE model), we will allow the treatment effect amongst compliers AND non-compliers to be freely estimated. All other sensitivity CACE model components will be identical to the primary CACE model.

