8.2 Definition of compliance

There are eight pregnancy circles antenatal sessions which are at approximately the following weeks of pregnancy: 16, 25, 28, 31, 34, 36, 38, 40. Theoretically participants have the chance to attend all of these eight sessions plus one session postnatally. However, because we wanted to capture those who initiated antenatal care after the first 12 weeks, some participants may miss the first session. Some women may also miss later sessions due to delivering early (WHO define moderate to late pre-term birth as 32 to 37 weeks meaning that women could miss up to four sessions). These factors have been taken into account when defining intervention compliance as in some cases participants may only have the opportunity to take part in three antenatal pregnancy circles sessions.

Intervention compliance is therefore defined as attending three or more antenatal circles. Our rationale for choosing three or more as the minimum (rather than 1 or 2 or 4 or more) is set out below.

Number of antenatal pregnancy circles sessions	Rationale for setting/not setting this number as cut-off point for compliance
1-2	Attending one or two sessions only means that most of their care will have been the same as standard one to one care. One or two sessions will not have been enough to establish friendships, benefit from midwife continuity, or participate in women led discussions. They may have learned how to self-check and be part of the circle's WhatsApp group if set up.
3	Reasonable to assume that 3 sessions is enough for women to understand (and be impacted by) the model, including self-checking; meeting other women; getting to know midwives; benefitting from woman-led discussion. Three sessions is less than half the antenatal visits for a primipara but for multipara this would represent half their antenatal visits (they have 6 antenatal appointments in standard care).
4	Highest confidence that participants would have received benefit and true experience of intervention: this represents half or more of antenatal follow-up appointments. Sufficient time for relationship-building. BUT
	Will exclude those participants who booked late and delivered early as non-compliers.

NB: In some developing countries, group care only offers 4 antenatal sessions so we can be confident that 4 sessions is enough to say they've received the intervention.

8.3 Impact of the pandemic on the Pregnancy Circles trial and dose definition *a) Overview*

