At the point of lockdown, 45 Pregnancy Circles had been run and completed, a further 58 circles were either already running or recruited to, and around six circles were waiting to be recruited to. Of the 58 already running or recruited to, 33 Circles have been assessed as providing a high or moderate dose of the COVID-19 adapted Pregnancy Circles during lockdown. From our target sample size of 1732 we had recruited 1624 women. We estimate that of the target sample size, 46% (n=795) received a 'full dose' of the intervention prior to the pandemic. A further 31% (n=531) had received a high or moderate 'dose' during the pandemic, 10% (n=176) had received a low or very low 'dose'; 7% (n=122) received no intervention; and 6% (n=108) were still to be recruited.

Pregnancy circle 'dose' offered

	Total groups	Details of dose offered	Total participants	Total intervention
	(Pregnancy Circles)		(int + control)	participants
Intervention as planned	45 (estimate)		795 (46% of sample size)	395
Partial intervention during lockdown	33	High 12 Circles (all had met face to face – 7 for 4 or more sessions; 5 who had met face to face fewer times but and then followed up with the provision of virtual groups/whatsapp/ continuity etc) Moderate 21 Circles (This category was either those that had met 3-4 times face to face and then had little in lockdown (8) OR Had met 1-2 times plus had other components (10). There were also 3 Circles that had not met face to face at all, but offered virtual circles)	531 (31%)	271 (117 high 154 moderate)
Low intervention during lockdown	13	Very low 6 Circles (Did not meet in person or virtually, but had 1 intervention component e.g. continuity of carer only) Low 7 Circles (2 Circles had met once, but nothing in place after; the remaining 5 did not meet face to	176 (10%)	92 (31 very low; 61 low)

		face nor offered any virtual groups, but had continuity and one other aspect eg Whatsapp group)		
Recruited but received no intervention	12	12 Circles; none of these circles had met face to face and no additional intervention components offered during lockdown. (most mid recruitment)	122 (7%)	63
Not yet recruited	-	-	108 (6%)	-

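### SAP 5.13 gives conflicting instructions for the CACE (compliers only versus two-stage least squares), and the 5.16.3 sensitivity model is not identified as specified

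*SAP*

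**What the plan says.** Section 5.13 introduces a "Complier Average Causal Effect (CACE) analysis estimating a 'per-protocol' treatment effect" and sets the analysis population: "The CACE analysis will repeat the primary outcome analysis using only those participants who complied". It then describes the target as women who comply, "compared to those who would have complied in the control group", and closes by saying that the estimates "will be generated using two-stage least squares (i.e. method of instrumental variable").

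Appendix 8.2 gives the threshold: "Intervention compliance is therefore defined as attending three or more antenatal circles". It places the eight sessions at "approximately the following weeks of pregnancy: 16, 25, 28, 31, 34, 36, 38, 40" and accepts that early delivery costs women sessions.

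Section 5.16.3 relaxes the exclusion restriction: "we will allow the treatment effect amongst compliers AND non-compliers to be freely estimated". All other components are to match the primary CACE model, which that section describes as setting the effect among non-compliers to zero.

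Dummy Tables 9 and 13 ask for an odds ratio as well as a risk difference. Section 5.15 lists controls who received the intervention as a known deviation, without a number.

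**The concern.** Two analysts could follow 5.13 and produce different quantities. One would drop circle-arm women with fewer than three sessions and rerun the primary model, which is a per-protocol contrast. The other would keep everyone and use allocation as an instrument. Only the second estimates a complier average causal effect.

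The first breaks randomisation in a predictable direction. Attendance is cut short by early loss or early delivery, and these are themselves failures on the healthy-baby composite. Section 5.13 sets the CACE beside the intention-to-treat estimate, so an inflated figure described as causal would be read as support for circles.

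The planned check on the central CACE assumption, in 5.16.3, does not state enough to be fitted. The tables also request an odds ratio that linear two-stage least squares does not supply.

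**Working it through.** **Inputs from the SAP.** Control rate 69%, planned difference 8 points (4.1.1); compliance is three or more circles, with the third session at about week 28 (8.2). **Assumed, because the SAP does not give them:** the proportion complying, the proportion of pregnancies ending before the third session, and the control crossover rate.

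**1. The two instructions in 5.13.** Let Z be allocation and D be attendance of three or more circles. Would-be compliance is not observed in controls, so the restriction can only be applied to the circle arm. Applied literally to both arms, it would leave no controls except any who crossed over. Once circle-arm non-compliers are removed, and if no control attends circles, D equals Z for everyone left. The instrumental-variable ratio then has denominator 1 − 0 = 1 and becomes the plain difference between circle-arm compliers and all controls. Running two-stage least squares on the restricted set therefore corrects nothing.

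**2. Bias with no true effect, from pregnancy length alone.** Let a proportion e of pregnancies end before the third session, all with outcome 'no', and let other non-attendance be unrelated to outcome. The healthy rate is 0.69 in all women and 0.69/(1−e) in those able to comply, so the spurious difference is 0.69·e/(1−e).

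| e (assumed) | Spurious difference, formula | Simulated, compliers only | Simulated, two-stage least squares on all women |
|---|---|---|---|
| 1% | 0.007 | 0.008 | 0.001 |
| 2% | 0.014 | 0.015 | 0.001 |
| 3% | 0.021 | 0.020 | −0.001 |
| 5% | 0.036 | 0.036 | −0.001 |

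A fuller simulation let attendance vary session by session (loss 1–3%, preterm birth 6–8%, attendance 60–85% per session while pregnant, all assumed). It gave +1.0 to +3.7 points.

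**3. Bias with no true effect, from any other difference.** If compliers would have had a healthy-baby rate g points above non-compliers without circles, and a proportion p comply, the spurious difference is (1−p)·g. With p = 70% and g = 5 to 15 points this is 0.3 × 5 = 1.5 to 0.3 × 15 = 4.5 points. With p = 90% it is 0.5 to 1.5 points.

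**4. Size when there is an effect.** With an intention-to-treat difference of 0.08 and p = 70%, the CACE is 0.08/0.70 = 0.114. The compliers-only contrast gives 0.114 + 0.015 = 0.129 to 0.114 + 0.045 = 0.159 over the same range of g.

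**5. Identification in 5.16.3.** With no crossover, the data give one equation, ITT = p·c + (1−p)·d, for two unknowns: the complier effect c and the non-complier effect d. In matrix terms, an intercept and one binary instrument have rank 2 against three parameters. At ITT = 0.08 and p = 0.70, c = (0.08 − 0.3d)/0.7, so these pairs fit equally well:

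| d | c |
|---|---|
| −0.10 | 0.157 |
| 0 | 0.114 |
| 0.08 | 0.080 |
| 0.10 | 0.071 |

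Adding site-by-allocation instruments, with compliance varying by site, restored full rank (16 of 16). The SAP specifies no such instruments.

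**6. A version that can be computed, allowing crossover.** Let p1 and p0 be the proportions attending three or more circles in the circle and control arms. Women who would not comply if offered circles make up 1−p1 and have effect d; controls who attend anyway are assumed to have no direct effect of allocation. Then ITT = (p1−p0)·c + (1−p1)·d, so CACE(d) = (ITT − (1−p1)·d)/(p1−p0). With ITT = 0.08, p1 = 0.70 and p0 = 0, d = 0, 0.02 and 0.04 give 0.114, 0.106 and 0.097. If p0 were 0.05 (assumed), d = 0 gives 0.08/0.65 = 0.123.

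**The case against.** The strongest reply is that the plan's intent is sound. Section 5.13 names the right target and the right estimator. Section 5.16.3 speaks of fixing the non-complier effect at zero, which is possible only if non-compliers are in the model. This stands. A reader might infer that the SAP simply prescribes a biased per-protocol analysis; the documents do not support that, because they contain both instructions. The defect is a contradiction, which the 'per-protocol' label makes easier to resolve the wrong way.

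The bias sizes rest on assumed inputs, and that stands too. Section 5.8 describes sessions from week 16 roughly every 17.5 days, which puts the third at about 16 + 35/7 = week 21. The two schedules need reconciling. On the earlier one, fewer pregnancies end too soon: if e were 1% rather than 3%, the formula falls from 2.1 to 0.7 points. Also, under 3.2 a live preterm birth with another component missing counts as missing, so the excluded women are nearly all, not all, 'no'.

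A reader might infer that the 5.16.3 model can never be fitted. That is too strong: further instruments or parametric assumptions could identify it. The SAP states none and says all other components are unchanged.

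A reader might also infer that the SAP contradicts its own exclusion restriction, since 4.1.2 halves the effect for a cohort that includes circles which "Had met 1-2 times plus had other components (10"). The halving is a planning average over 33 circles. Appendix 8.3 scores what circles were offered, whereas compliance is each woman's own attendance. Ten of the 21 moderate-dose circles would hold about 10/21 × 154 = 73 intervention women, or 8% of roughly (2190 − 298)/2 = 946 per arm. Giving all of them a 4-point effect as non-compliers moves the CACE from 0.114 to (0.08 − 0.078 × 0.04)/0.70 = 0.110. That is a reason to test the assumption, and to say whether virtual sessions count, but it does not show the assumption to be false.

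**Conclusion.** The point holds as an internal contradiction together with an under-specified sensitivity model. Followed literally, the compliers-only sentence gives a per-protocol contrast tilted toward circles, by roughly 1 to 4 points with no true effect, under assumed early-loss, preterm and attendance rates. Two-stage least squares on all women is centred near 0 under the same assumptions. The 5.16.3 model is not identified with allocation as the only instrument. Linear two-stage least squares also gives no odds ratio for the CACE entries in Tables 9 and 13.

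Severity is moderate. The CACE supplements the main analysis, and the intention-to-treat estimate, its p-value and the trial's main conclusion do not depend on it.

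**What to change.** **Section 5.13.** Delete the compliers-only sentence and the 'per-protocol' label. State that two-stage least squares is run on all women in the primary analysis population, with allocation as instrument and attendance of three or more circles as exposure, coded from actual attendance in both arms. Include English level and site as covariates, and cluster standard errors on circle, each control being her own cluster. State whether virtual sessions count as attendance.

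**Section 5.16.3.** Replace the model with CACE(d) = (ITT − (1−p1)·d)/(p1−p0) over a stated grid for d (for example 0, 2 and 4 points), with p1, p0 and d defined as in the working and the assumption about controls who attend written down. It reduces to (ITT − (1−p)·d)/p if no control attends. If a freely estimated model is preferred, its added instruments or assumptions must be stated.

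**Tables 9 and 13.** Report the CACE as a risk difference only. Keep the odds ratio in the intention-to-treat row of Table 9, because 5.8 names it as a summary measure.

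**Cost.** A short SAP amendment and changed table headings. No new data collection is proposed beyond circle attendance in both arms, and the replacement sensitivity analysis is closed-form.

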5.14 Dose response analysis

We will explore the dose-response relationship between the number of sessions attended and the primary outcome in the intervention arm. The scale of this attendance variable is 0-8 where 0 = no antenatal circles attended and 8 = 8 antenatal circles attended. Dose will be used as a continuous variable assessed in a model fitted on intervention group participants only.

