3.2 Primary outcome

The "healthy baby" composite consists of the following 4 components:

- 1. Live baby (i.e. no pregnancy loss before 24 completed weeks, no stillbirth after 24 completed weeks of pregnancy and no neonatal death within 28 days of the birth)
- 2. Born at term (≥ 37 weeks + 0 days)
- 3. Appropriate weight for gestational age (GROW centile >9.99 & <90.01)*
- 4. Not admitted to a neonatal care unit (which includes Intensive Care Unit, SCBU and High Dependency Unit, but NOT transitional care)

A baby is considered a "healthy baby" only if the answer to all above questions is "yes", otherwise "no" (binary outcome measure). The primary outcome will be considered missing if any of its components are missing apart from the following exception: If Live baby is recorded as 'no' then the healthy baby outcome is 'no' regardless of whether other components are missing.

* The GROW centile macro version 8.0.6.2 will be used for component 3. Appropriate weight for gestational age. It is multidimensional and includes: maternal height and weight, ethnic origin, parity at booking, gestational age, baby alive (yes/no), baby gender and weight (g).

Note: at the grant application stage, the secondary outcome, spontaneous vaginal delivery (SVD) was defined as the primary outcome for the trial. However, following advice from and discussion with various stakeholders the "healthy baby" composite outcome was deemed a more suitable primary outcome for this project and chosen prior to commencement of the trial.

3.3 Secondary Outcomes*:

- 1. Spontaneous vaginal delivery (SVD)** defined as a woman who delivers vaginally (binary: for SVD, yes favoured)
- 2. Women's empowerment using pregnancy-related empowerment scale (continuous: sum of individual items with scores ranging from 16-64; higher scores are favoured)
- 3. Women's satisfaction with maternity care using *NHS* Friends and family test (continuous: score on one question with scores ranging from 1-5; lower scores favoured)
- 4. Breast feeding initiation (binary: did mother ever initiate breastfeeding, yes favoured --> however, possible different responses for descriptive analysis)
- 5. Mental wellbeing using Short Warwick-Edinburgh Mental Wellbeing Scale (continuous: total score ranges from 7-35, higher scores indicate higher positive mental wellbeing)

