5.16.6 Sensitivity analysis of the dose-response relationship

In this analysis, we will change the assumptions regarding missing data in two steps: 1) we will consider that women attended all sessions where there is a missing value 2) we will impute the median and then mean value for women where the number of session(s) is missing.

6. Other analyses, data summaries, and graphs

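### The dose-response analysis uses a raw session count that early delivery and pregnancy loss cut short, so its slope is biased towards benefit

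*SAP*

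**What the plan says.** Section 5.14 plans a regression of the primary outcome on attendance: "We will explore the dose-response relationship between the number of sessions attended and the primary outcome in the intervention arm". On the model it says: "Dose will be used as a continuous variable assessed in a model fitted on intervention group participants only". The scale is the number of antenatal circles attended, 0 to 8. The section names no covariates, and the general rule in 5.5 adjusts for centre and English ability only. Dummy Table 10 reports a coefficient, a 95% confidence interval and a p-value.

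Appendix 8.2 puts the eight sessions at approximately weeks "16, 25, 28, 31, 34, 36, 38, 40" and adds: "Some women may also miss later sessions due to delivering early". It uses this to justify a compliance cut-off of three sessions. Section 5.14 does not carry it over.

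Section 3.2 counts a baby as healthy "only if the answer to all above questions is" yes. One component is "Born at term (≥ 37 weeks + 0 days"). For losses, "If Live baby is recorded as 'no' then the healthy baby outcome is 'no' regardless of whether other components are missing".

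Section 5.16.6 varies only how missing attendance is filled in. Its first step reads: "we will consider that women attended all sessions where there is a missing value". Its second imputes the median and then the mean.

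**The concern.** The outcome and the exposure share a cause that has nothing to do with the intervention: when the pregnancy ends. A woman who delivers early fails the composite by definition and also loses the chance to attend later sessions. A woman who reaches term keeps both the chance of a yes and the chance of a high count. This is reverse causation (an immortal-time problem) on top of the usual self-selection into attendance. Adjusting for centre and English ability does not touch it, and neither does 5.16.6, because observed counts shortened by early birth stay as they are.

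At stake is the reading of Tables 10 and 15. Part or all of an apparent gain in healthy babies per extra session could be an artefact, and no planned analysis would show this. Implementation in the NHS is among the trial's objectives (section 2), and such a slope could easily be cited in that context.

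**Working it through.** The plan gives no figure to reproduce in 5.14, so the check is in three steps.

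**1. Sessions available, on the 8.2 schedule.** The weeks are approximate, so these ceilings are approximate too. If each available session is attended with probability 0.7 (an assumption), the expected counts are:

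| Pregnancy ends | Sessions available | Expected count | Outcome |
|---|---|---|---|
| Loss before 24 weeks | 1 | 1 × 0.7 = 0.7 | no by definition |
| Birth between the week-31 session and week 32 | 4 | 4 × 0.7 = 2.8 | no by definition |
| Birth between the week-36 session and 37+0 | 6 | 6 × 0.7 = 4.2 | no by definition |
| Birth between the week-38 and week-40 sessions | 7 | 7 × 0.7 = 4.9 | yes possible |
| Birth after the week-40 session | 8 | 8 × 0.7 = 5.6 | yes possible |

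Low counts are therefore enriched with certain failures.

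**2. Size when attendance has no effect.** Inputs from the SAP:
- 69% healthy (4.1.1).
- A background preterm rate of 5.6% (8.1).
- Analysed intervention women (4.1.2 and 4.1.1): (2190 − 298)/2 = 946, and 946 × 0.9 ≈ 851 after 10% drop-out.

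Assumptions not in the SAP are the attendance rate, the loss rate and the distribution of gestation at birth. Clustering is ignored. Each session before birth is attended at random, a preterm birth or loss gives a no, and the fitted model is logit Pr(healthy) = a + b × sessions, with true b = 0. With 5.6% preterm and no loss, an overall 69% implies 0.69/0.944 = 73% healthy among term births. Entries are the mean odds ratio per session and the percentage of 500 runs with a significant positive slope (n = 850):

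| Schedule, loss rate | 50% attend | 70% attend | 90% attend | Varies between women, mean 60% |
|---|---|---|---|---|
| 8.2, no loss | 1.12 (54%) | 1.18 (89%) | 1.38 (nearly 100%) | 1.06 (37%) |
| 8.2, 1% loss | 1.17 (87%) | 1.25 (98%) | 1.46 (100%) | 1.09 (69%) |
| 17.5-day, no loss | 1.01 (4%) | 1.03 (8%) | 1.08 (16%) | 1.01 (5%) |
| 17.5-day, 1% loss | 1.07 (24%) | 1.10 (43%) | 1.24 (88%) | 1.03 (14%) |

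At 70% attendance on the 8.2 schedule without losses, 47% of women with 0–2 sessions have a healthy baby against 72% of those with 5 or more, with no true effect. Among term births only, the odds ratio is about 1.00, which isolates the cause. On the 8.2 schedule, 8% preterm with 1% loss gives 1.11 (varying attendance) to 1.60 (90% attendance). With 3% preterm and no loss the range is 1.03–1.21, significant in 17–80% of runs.

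The bias shrinks when more of the variation in attendance comes from elsewhere. Section 8.3 counts 271 intervention women in circles partly delivered during lockdown, and they stay in the primary population: 271/946 = 29%. Adding truncation at a random week for 29% of women, due dates spread by ±2 weeks within a circle, and mean attendance of 50–75% varying between women, the odds ratio is about 1.03–1.10. Roughly 14–90% of trials are significant over 5.6–8% preterm and 0–1.5% loss.

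**3. The two schedules.** In 8.2 the span is 40 − 16 = 24 weeks, or 168 days over 7 gaps: 24 days on average. The estimand table in 5.8 gives about 17.5 days from week 16, so session 8 falls at 16 + 7 × 2.5 = 33.5 weeks. The two cannot both describe the programme, and the table above shows how much the bias depends on which applies.

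**The case against.** The strongest reply is that 5.14 only sets out to explore, is confined to the intervention arm and leaves the intention-to-treat analysis alone; no section ties a decision to it. That stands, and it limits the weight of the point. But 5.12 labels the subgroup analyses as hypothesis-generating only, and 5.14 carries no such label.

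A reader might infer that the analysis must show benefit, or that a significant result is guaranteed. The documents do not support that. The bias is upward, but other influences on attendance could add to it or offset it, and under plausible conditions most null trials would not reach significance.

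A reader might also treat the ceilings (at most six sessions for a preterm birth, seven or eight only at term) as hard facts. They are not: the weeks in 8.2 are approximate, and a circle mixes due dates within about a month (4.2), so a given session falls at different gestations for different members.

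Finally, the fill-in rule in 5.16.6 might be read as adding to the bias. The wording is open: it may mean counting each missing session as attended, or scoring the woman at eight. If it means eight, giving full dose to women who delivered early would pull the slope down. The fair criticism is narrower: the rule has no cap at the end of pregnancy and does not address shortened observed counts.

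**Conclusion.** The point holds as a bias towards benefit in an exploratory analysis, and it should be fixed. The direction follows from the SAP's own definitions on the 8.2 schedule. The size does not: it depends on attendance, loss rate and gestation, which the SAP does not give.

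With about 850 women, 5.6–8% preterm and 0–1.5% loss, the spurious odds ratio per session is about 1.12–1.50 under uniform attendance, reaching 1.60 only in the most extreme combination tried. The range of 1.03–1.10 is the better guide to this trial, because it allows for uneven attendance, due-date spread and the pandemic. On the 17.5-day spacing it runs from 1.01–1.08 without losses to 1.03–1.24 with 1% loss. The primary comparison of the arms is unaffected.

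**What to change.** - **5.14, preferred:** replace the raw count with sessions attended divided by sessions scheduled for the woman's circle before her pregnancy ended. Exclude women with no session available and report their number. In the null simulations this gives an odds ratio of 0.93–1.04 over the full 0–1 range, with 3–8% of runs significant.
- **5.14, alternative:** a landmark. Count dose up to a fixed week, for example the week-28 session, among women still pregnant at that same week, with the full composite as outcome. The null odds ratio per session is then 0.98–1.01, with 2–8% significant. The restriction must sit at the landmark week. Requiring women to be still pregnant at 37+0 would condition on a component of the outcome and drop preterm birth from the question.
- **5.16.6:** say whether the first step applies per session or to the whole count, and cap imputed attendance at the sessions that took place before the pregnancy ended.
- **Reporting:** describe the result as associational in the text and in Tables 10 and 15.
- **5.8 and 8.2:** reconcile the session spacing.

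**Cost:** mostly SAP wording, but the denominator needs the dates of each circle's sessions, or the scheduled weeks as a proxy once the two sections agree. The landmark also needs attendance by session. The SAP does not say whether either is held. The landmark version discards later sessions and pregnancies that ended before the landmark, so it answers a narrower question.
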